4.7 Demographics and Baseline Characteristics

Demographic and baseline characteristics will be summarised and listed for all patients in the Safety analysis set by dose level/cohort as appropriate:

- Demographic characteristics (age [years], age group [< 65 years; ≥ 65 years], sex [female; male], race, ethnicity and country); height (cm), weight (kg)
- Any other patient/disease characteristics at baseline as specified below:
 - Disease type,
 - WHO classification of acute leukaemia,
 - Molecular and cytogenetic characteristics of AML/ALL,
 - Eastern Cooperative Oncology Group (ECOG) performance status,
 - Extramedullary disease will be listed for target/non-target lesions for ALL.

4.8 Medical/Surgical History

Medical history and surgical history will be coded using Medical Dictionary for Regulatory Activities (MedDRA). Disease related medical history will be listed and the number and percentage of patients with any disease-related medical history will be summarised for the Safety analysis set by system organ class (SOC) and preferred term (PT), by dose level/cohort and overall as appropriate.

Surgical history will be summarised, if applicable.

4.9 Prior Treatments for Leukaemia

Prior therapies are defined as started and stopped prior to the first dose of the study treatment based on imputed start and stop dates. Incomplete therapy start and stop dates will be imputed as detailed in section 4.3.4.1.

Radiotherapy and all cancer therapies prior to the study will be listed.

The following summaries will be produced for prior therapies for leukaemia disease under study:

- Prior anti-cancer therapy class
- Prior anti-cancer radiotherapy
- Number of prior lines of anti-cancer therapy
- Number of prior regimens of anti-cancer therapy
- Anti-cancer therapy agent by ATC and generic drug name

Treatment status (Consolidation, Palliative, Maintenance, Induction Therapy) will be listed.

In addition to prior therapies for leukaemia, post-study cancer treatment will be listed. Post-study anti-cancer treatments are defined as treatments started after a patient discontinued study treatment.

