5.1 Core Inclusion Criteria

The inclusion criteria that are applicable to all modules in the study are described in this section. Additional module-specific criteria are included in the specific modules. If specific module criteria are more stringent than the core inclusion criteria, the module criteria must be met.

Informed Consent

- 1 Provision of signed and dated written informed consent prior to any study-specific procedures, sampling, and analyses. Informed consent is described in Appendix [A 3](#), which includes compliance with the requirements and restrictions listed in the informed consent form (ICF) and in this protocol.
 - If a patient declines to participate in optional exploratory research and/or genetic component of the study, there will be no penalty or loss of benefit to the patient and he/she will not be excluded from other aspects of the study.

Age

- 2 Patient must be aged \geq 18 years, at the time of signing the informed consent. In some countries parental consent may be required in addition to an assent form for patients who are 18 years of age.

Patient and Disease Characteristics

- 3 Diagnosis of AML, ALL, or intermediate or higher risk myelodysplastic syndrome (MDS; Part A only), which is histologically proven based on criteria established by the World Health Organization (WHO) as documented by medical records.
- 4 Patients must have received at least one prior line of therapy, and an established standard of care with proven benefit, and for which the patient is eligible, must not be available at the time of enrolment.
- 5 For AML or ALL patients, documented active disease requiring treatment that is relapsed or refractory defined as:
 - Recurrence/relapse of disease after response to prior line(s) of therapy
 - Progressive disease (refractory) on/after completion of the treatment regimen preceding entry into the study

- 6 For intermediate and higher risk MDS, documented active disease is defined as:
 - Patients with > 10% blasts, and/or
 - MDS with intermediate, high, or very high risk (risk score > 3) per the Revised International Prognosis Scoring System (IPSS-R) ([Appendix O](#)).
- 7 Eastern Cooperative Oncology Group (ECOG) performance status ≤ 2 . Performance status must not have deteriorated by ≥ 2 levels within 2 weeks after providing informed consent.
- 8 Predicted life expectancy ≥ 8 weeks.

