4.3.4.1 Imputations of Partial Dates

Concomitant medication and adverse events start dates

- Missing day: imputed with the 1st of the month, unless month and year are the same as month and year of first dose of study treatment, then impute with first dose date.
- Missing day and month: imputed with the 1st of January unless the year is the same as the year of first dose of study treatment, then imputed with first dose date.
- Completely missing: imputed with date of first dose of study treatment, unless the end date suggests it could have started prior to this in which case it is imputed 1st January of the same year as at the end date.

When imputing a start date care should be taken to ensure the start date is sensible, i.e., prior to the end date.

Concomitant medication and adverse events end dates

- Missing day: imputed with the last day of the month, unless month and year are the same as month and year of last dose of study treatment, then imputed with the last treatment date in that month.
- Missing day and month: imputed with the 31st of December unless the year is the same as the year of last dose of study treatment, the imputed with the last treatment date in that year.
- Completely missing: no date imputed (the event is assumed to be ongoing).

No study day or duration will be calculated for imputed dates.

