4.10 Previous and Concomitant Medications and Other Treatments

Treatments received prior to, concomitantly or post-treatment will be coded using the World Health Organisation-Drug Dictionary (WHODRUG) and will be classified by Anatomical Therapeutic Chemical (ATC) categories.

For the purpose of inclusion in prior and/or concomitant medication or therapy summaries, incomplete medication or radiotherapy start and stop dates will be imputed as detailed in section 4.3.4.1.

Prior medications, concomitant and post-study medications are defined based on imputed start and stop dates as follows:

- Prior medications are those that started and stopped prior to the first dose of the study treatment
- Concomitant medications are those with a stop date on or after the first dose date of study treatment (and could have started prior to or during treatment)
- Post-study medications are those with a start date after the last dose of the study treatment.

All concomitant medication will be listed by patient and will include the reported name, coded name, (ATC), route of administration, dose, frequency, start date/time, duration and indication (PT). Concomitant medication will be summarised by ATC and PT, dose level/cohort as appropriate.

All prior, concomitant and post study treatment medication data (including surgical procedures) will be listed. Missing coding terms (ATC or PT) will be listed and summarised as uncoded terms.

All listings and tables will be based on the Safety analysis set.

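### SAP 4.9 classifies prior leukaemia therapy on late-imputed stop dates, so recent regimens with certain incomplete dates drop out of the prior-therapy summaries

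*SAP*

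**What the plan says.** SAP 4.9 (Prior Treatments for Leukaemia) sets the definition: "Prior therapies are defined as started and stopped prior to the first dose of the study treatment based on imputed start and stop dates". It adds: "Incomplete therapy start and stop dates will be imputed as detailed in section 4.3.4.1". The summaries built on it are therapy class, radiotherapy, number of lines, number of regimens, and agent by ATC and generic name. The section also provides for a listing of all cancer therapies and radiotherapy given before the study.

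SAP 4.3.4.1 has no rule for prior therapy. Its stop-date rules stand under the label "Concomitant medication and adverse events end dates" and run as follows:

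- Day unknown: "Missing day: imputed with the last day of the month", or the last treatment date in that month if it is the month of last dose.
- Day and month unknown: "imputed with the 31st of December unless the year is the same as the year of last dose of study treatment", in which case the last treatment date in that year is used.
- Nothing known: "Completely missing: no date imputed (the event is assumed to be ongoing".

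Partial start dates in the month or year of first dose are set to the first dose date. The only plausibility check concerns start dates, which should come before the end date.

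SAP 4.10 says "Concomitant medications are those with a stop date on or after the first dose date of study treatment", again on imputed dates. Protocol 5.1, inclusion criterion 4, says "Patients must have received at least one prior line of therapy".

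**The concern.** Late imputation of a stop date is the cautious choice for a concomitant drug or an adverse event, because it avoids missing an overlap with study treatment. For a regimen known to have ended before dosing, it works the wrong way. The rule can move the stop date to or past first dose, and the regimen then no longer counts as prior.

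The most recent line is the most exposed, because its end is closest to first dose. In a relapsed or refractory population, the number and type of prior lines are basic context for reading the CR+CRi rate. Under SAP 7.1, dose levels may hold as few as 3 and up to 12 patients, so one lost line shows in the table. A patient with a single affected line would be tabulated with none, against the entry criterion.

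**Working it through.** The documents give no figure on this point, so there is none to reproduce. The check applies the SAP rules as written.

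**Notation.** F = first dose date, L = last dose date (L ≥ F), g = days from the true stop of the prior regimen to F (g > 0).

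**Which stop dates fail**

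- Day missing, stop in the month of F. If L is in that month, the imputed date is L, which is ≥ F. If not, it is month-end, also ≥ F. Never prior.
- Year only, stop in the year of F. If L is in that year, the imputed date is L ≥ F. If not, it is 31 December ≥ F. Never prior.
- Wholly missing. Treated as ongoing, however long ago the regimen ended. Never prior.
- Day missing in an earlier month, or year-only in an earlier year. The imputed month-end or 31 December is still before F. Remains prior.

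**Worked example**, F = 20 March 2022, L = 24 April 2022:

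| Recorded stop | Imputed stop | Result under 4.9 |
|---|---|---|
| March 2022 | 31 March 2022 | not prior |
| 2022 | 24 April 2022 | not prior |
| missing | ongoing | not prior |
| February 2022 | 28 February 2022 | prior |
| 2021 | 31 December 2021 | prior |

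**Start dates.** A partial start in the month or year of F becomes F and fails the started-before test. If a complete stop date before F is on record, the start-date plausibility check should pull the start back. If the stop is also imputed late, that check has nothing to catch.

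**How often a partial stop date is misclassified.** Assume F is uniform over the 365 days of a year and g is fixed.

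- Day missing: the stop falls in the month of F when the day of the month of F exceeds g. Share = Σ over months of max(0, days in month − g) / 365, which is (365 − 12g)/365 for g ≤ 28.
- Year only: share = (365 − g)/365 for g ≤ 365.

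| Gap g (days) | Day missing | Year only |
|---|---|---|
| 7 | 281/365 = 77.0% | 358/365 = 98.1% |
| 14 | 197/365 = 54.0% | 351/365 = 96.2% |
| 21 | 113/365 = 31.0% | 344/365 = 94.2% |
| 28 | 29/365 = 7.9% | 337/365 = 92.3% |
| 60 | 0% | 305/365 = 83.6% |
| 90 | 0% | 275/365 = 75.3% |
| 180 | 0% | 185/365 = 50.7% |
| 365 | 0% | 0% |

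A direct enumeration with dosing on Days 1, 4, 8 and then weekly gave the same shares for 3, 7 and 20 doses.

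**Share of patients.** The proportion of partial dates is not in the documents. If 10% to 30% of last regimens had a partial stop date (an assumption) and the gap were 14 days, the share losing that line would be:

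- all day-missing: 0.10 × 54.0% to 0.30 × 54.0%, about 5% to 16%;
- all year-only: 0.10 × 96.2% to 0.30 × 96.2%, about 10% to 29%.

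At a 28-day gap, the day-missing range falls to about 0.8% to 2.4%.

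**The case against.** The strongest reply is that the gap is narrow and its consequences small. Much of that stands. The listing of prior cancer therapies is kept, so no record is lost. No hypotheses are tested, there is no covariate adjustment, and the DLT, adverse event and response definitions do not use prior lines. The Part B cohorts, whose entry depended on a maximum number of prior lines, were never opened.

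Four stronger inferences are tempting, and the documents do not support them.

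- A reader might infer that every partial stop date is pushed past first dose. Dates in an earlier month or year are not.
- A reader might infer from the 14-day washout that last regimens normally end in the month of first dose. Protocol 5.2, criterion 14, gives 14 days or 5 half-lives, whichever is shorter, for anticancer agents, but 3 weeks for radiotherapy and 4 weeks for immunotherapies and cellular therapies. A washout is also a minimum gap, not the expected one.
- A reader might equate the share of partial dates with the share of patients losing a line. The date must also fall in the month or year of first dose, or be wholly missing.
- A reader might infer that these regimens will appear as disallowed on-study drugs under SAP 4.11 or as Deviation 3 under SAP 4.6.2.1. They would meet the 4.10 definition of concomitant only if prior-therapy records feed those datasets, and the eCRF structure is not shown. Protocol Section 8 collects prior anticancer treatments at screening, which suggests separate capture. SAP 4.6.2 has deviations judged case by case.

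The reply does not remove the main point: no passage caps a prior-therapy stop date before first dose or exempts these records from SAP 4.3.4.1.

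**Conclusion.** The rule is wrong as written for a defined set of records: stop dates without a day in the month of first dose, year-only stop dates in the year of first dose, and wholly missing stop dates. For these the misclassification is certain and follows from the SAP's wording alone. The 4.9 summaries would undercount lines, regimens, classes, agents and radiotherapy, and a patient whose every line is affected would show none.

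How often this happens rests on three things the documents do not give: the share of partial dates, the gap from last regimen to first dose, and the spread of first-dose dates (taken as uniform above). The effect is confined to descriptive baseline tables, extending to the concomitant tables only if the datasets are joined. It is a modest point, but worth correcting because the tables could otherwise contradict eligibility.

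**What to change.** Amend SAP 4.9 so that prior leukaemia therapy is identified by the eCRF prior-anticancer-therapy record, not by dates imputed under SAP 4.3.4.1. For those records:

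- Cap any imputed partial start or stop date at the day before first dose, except where a full recorded date or an explicit ongoing entry shows that treatment continued (for example the hydroxyurea or steroids that the protocol permits).
- Query wholly missing stop dates before database lock.
- Do not use capped dates to judge washout deviations, since the cap could hide a real breach.

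Keep SAP 4.3.4.1 for concomitant medications and adverse events. With either the cap or classification by source record, misclassification from this rule falls to zero at every gap. The cost is about one sentence in the SAP and a minor programming change.

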4.10 Previous and Concomitant Medications and Other Treatments

Treatments received prior to, concomitantly or post-treatment will be coded using the World Health Organisation-Drug Dictionary (WHODRUG) and will be classified by Anatomical Therapeutic Chemical (ATC) categories.

For the purpose of inclusion in prior and/or concomitant medication or therapy summaries, incomplete medication or radiotherapy start and stop dates will be imputed as detailed in section 4.3.4.1.

Prior medications, concomitant and post-study medications are defined based on imputed start and stop dates as follows:

- Prior medications are those that started and stopped prior to the first dose of the study treatment
- Concomitant medications are those with a stop date on or after the first dose date of study treatment (and could have started prior to or during treatment)
- Post-study medications are those with a start date after the last dose of the study treatment.

All concomitant medication will be listed by patient and will include the reported name, coded name, (ATC), route of administration, dose, frequency, start date/time, duration and indication (PT). Concomitant medication will be summarised by ATC and PT, dose level/cohort as appropriate.

All prior, concomitant and post study treatment medication data (including surgical procedures) will be listed. Missing coding terms (ATC or PT) will be listed and summarised as uncoded terms.

All listings and tables will be based on the Safety analysis set.

4.11 Disallowed Concomitant Medications

Patient may have received prohibited concomitant medication as detailed in Section 6.5.2 of the study protocol or any other concomitant medication which, upon physician review of all medications and procedures prior to database lock, is considered to have a potential effect on study outcomes.

Disallowed concomitant medications will be summarised and listed.

4.12 Efficacy Evaluation

Refer to the individual modules.

4.13 Pharmacokinetics

4.13.1 Pharmacokinetic Concentrations

Plasma concentrations of total and released AZD4320 will be listed by actual and relative (to dose administration) sampling time. The following summary statistics will be presented for the concentrations and PK parameters at each time point separately per cohort and actual dose level:

- n below LLOQ (only for concentrations)
- Geometric Mean (gmean, calculated as $\exp[\mu]$, where μ is the mean of the data on a logarithmic scale)
- Geometric CV% (gCV, calculated as $100 \sqrt{[\exp(s^2)-1]}$, where s is the standard deviation of the data on a logarithmic scale)
- Arithmetic Mean
- Arithmetic SD
- Minimum
- Median
- Maximum
- Number of observations

In listings, concentrations below the lower limit of quantification (LLOQ) will be presented as BLQ. In listings and tables where the terms BLQ or LLOQ are included, the LLOQ (numerical value) will be included in a footnote.

For the calculation of statistics, concentrations that are BLQ will be handled as follows at each time point:

- If $\leq 50\%$ of the concentrations are BLQ, all BLQ values will be set to the LLOQ, and all descriptive statistics will be calculated.
- If $>50\%$, but not all, of the concentrations are BLQ, the geometric mean, geometric CV, arithmetic mean, and arithmetic SD will be reported as 'NC' (not calculable). The maximum value will be reported from the individual data, and the minimum and median will be set as 'BLQ'.
- If all concentrations are BLQ, no descriptive statistics will be calculated. 'NA' (not applicable) will be presented for geometric CV, and arithmetic SD, and 'BLQ' will be presented for geometric mean, arithmetic mean, median, minimum, and maximum.

For PK concentration and parameter data, if there are <3 values available at a time point, only the maximum, minimum, and n will be reported; the remaining descriptive statistics will be reported as 'NC'. Concentrations that are BLQ are considered a value.

Missing samples will be reported as no sample ("NS") and excluded from analysis.

Source data shall be used in all derived PK concentrations without prior rounding

The following figures, in black and white, will be generated for total and released AZD4320, and its metabolites (if available and appropriate):

- Patient Profiles, Plasma Concentration Time Data – Linear Scale
- Patient Profiles, Plasma Concentration Time Data - Semi-Logarithmic Scale
- Gmean (\pm gSD), Plasma Concentration Time Data (gSD calculated as $\exp[\mu \pm s]$)
- Gmean, Plasma Concentration Time Data - Semi-Logarithmic Scale

Individual figures will be plotted using concentration versus actual time, and mean figures will be plotted using concentration versus nominal time, by treatment or dose level and cycle/PK day, as needed.

4.13.2 Pharmacokinetic Parameters Calculation and Summary

Derived PK parameters will be summarized by cycle, separately per cohort and actual dose level. The following summary statistics will be presented for the estimated PK parameters, as appropriate:

- Gmean (calculated as $\exp[\mu]$, where μ is the mean of the data on a logarithmic scale)
- gCV (calculated as $100 \sqrt{[\exp(s^2)-1]}$, where s is the standard deviation of the data on a logarithmic scale)
- Arithmetic mean calculated using untransformed data
- Arithmetic SD calculated using untransformed data
- Minimum
- Median
- Maximum
- Number of observations

The descriptive statistics for diagnostic parameters are n, arithmetic mean, SD, median, min, and max.

The following rules will be followed with regards to the number of decimal places and presentation of data in the tables and listings for PK parameters:

- Individual PK parameters will be presented to four significant digits, with the exception of t_{max} , which will be presented to two decimal places.

- Parameters derived directly from source data (e.g. C_{max}) shall be reported with the same precision as the source data (if this is not four significant digits).
- The mean, geometric mean, median and SD values will be reported to four significant digits, all other descriptive statistics will be reported to three significant digits except for CV% which will be presented to one decimal place.
- For t_{max} the minimum and maximum will be presented to two decimal places and all other descriptive statistics will be presented to three decimal places.
- Estimates and confidence intervals in the form of percentages will be presented to two decimal places.

4.13.3 Criteria for Handling Concentrations Below the Limit of Quantification or Missing Concentrations in Pharmacokinetic Analysis

For the non-compartmental analysis (NCA) and individual plot, if a BLQ value occurs before the first measurable concentration, it will be treated as zero. Thereafter, BLQ values will be treated as missing for PK analysis, with special situations described below. The following rules apply with special situations defined below:

- Where 2 or more consecutive concentrations are BLQ at the end of a profile, the profile will be deemed to have terminated and any further quantifiable concentrations will be set to missing for the calculation of the PK parameters unless they are considered to be a true characteristic of the profile of the drug.
- If an entire concentration-time profile is BLQ, the profile will be excluded from the PK analysis.
- If a pre-dose measurement for the first dose of cycle 1 is missing it will be set to zero for a single dose, or to the minimum observed concentration for a repeat dose.

4.13.4 Treatment of Outliers in Pharmacokinetic Analysis

If a value is considered to be anomalous due to being inconsistent with the expected PK profile, it may be appropriate to exclude this point from the PK analysis. However, the exclusion of data must have strong justification and will be documented in CSR.

Quantifiable pre-dose concentration values in the first dosing of cycle 1 (i.e., the first ramp-up dose) will be considered anomalous and set to missing for the PK analysis.

